#### Dosing

Subjects will take an 8.9 mg dose of pitolisant (two 4.45 mg pills) or placebo once per day on day 1 through 7, beginning 12 days prior to the alcohol challenge. Subjects will then take a 17.8 mg dose of pitolisant (one 17.8 mg pill) or placebo once daily on days 8 through 12. This dose was chosen because it is consistent with the clinical dose range of this drug when it is used for treating narcolepsy.

### Medication Storage

Medication will be stored in the Investigational Pharmacy at room temperature (within the range of 59°F to 86°F) in a secured area until the time that medication is needed for study subjects. Stability and expiry will be monitored by IPS according to the labelling of the medication from the manufacturer.

#### Medication Labeling

The study number will be preprinted on each bottle label. The label will include the drug name (e.g., "Pitolisant 4.45 mg", "Pitolisant 17.8 mg" or "placebo"). The label will also have a randomization number, the number of tablets contained in the bottle, storage conditions, the 24/7 phone number of the clinical site, and places to record the subject number and the date dispensed. Additional fields may be added to this label to meet any regulatory requirements as determined by IPS.

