#### 5 Study Design

This is a double-blind, randomized, placebo-controlled, crossover design trial that will test the effect of pitolisant on alcohol self-administration and craving following a priming dose of alcohol. An established human laboratory self-administration methodology developed by O'Malley and her colleagues will be followed. The O'Malley self-administration methodology entails subjects consuming a priming drink of alcohol and subsequently participating in two one-hour self-administration sessions. In each session subjects receive four alcoholic drinks which

they may either drink, or otherwise receive compensation for not consuming. Confirmation of the validity of this approach as a method for screening for medications to treat AUD include the finding that pre-treatment with naltrexone significantly reduced alcohol consumption when the O'Malley methodology was used. Using this method, our group has found that the anticonvulsant zonisamide reduces alcohol consumption in non-treatment seeking social drinkers. We later confirmed that the administration of zonisamide decreases alcohol consumption in subjects with AUD in a double-blind randomized clinical trial as have other investigators. Testing pitolisant using this self-administration methodology is the next logical step in drug development given the strong evidence that the H-3 receptor inverse agonist/antagonists reduce drinking in animal models. The human laboratory-based alcohol self-administration methodology is cost effective and time-efficient for testing novel drug candidates for AUD treatment.

*Subjects:* Heavy-drinking subjects will be enrolled to increase the potential generalizability of these findings to a clinical AUD population. Subjects will be recruited through advertising, study flyers, internet postings, and an established subject registry at Boston Medical Center. Interested subjects will be screened by telephone to determine initial eligibility prior to the baseline assessment.

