## 8 Study Intervention

## Study Medication

Study medication will be packaged by the BMC Investigational Pharmacy Service. Pitolisant 4.45 mg pills will be over-encapsulated with 25 mg of riboflavin and pitolisant 17.8 mg pills will be over-encapsulated with 50 mg of riboflavin which will serve as a tracer of medication compliance using urine obtained on the day of the alcohol challenge. Matching placebo will also be packaged using lactose and 25 mg (4.45 mg pill) or 50 mg (17.8 mg pill) of riboflavin. Medication will be dispensed to each subject in two bottles. One bottle will contain 14 pills of pitolisant (4.45 mg) or placebo and the other bottle will contain 5 pills of pitolisant (17.8 mg) or placebo. Capsule size required will be determined by IPS with the goal of a minimum capsule size needed for over-encapsulation. If a subject reports losing (or destroying) study medication, a replacement prescription will be written by one of the study physicians and the BMC Investigational Pharmacy will dispense additional medication to replace the lost (or destroyed) medicine.

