#### Medication Blinding and Unblinding

Study medication and placebo capsules will be identically matched in appearance and the bottle labels will not reveal the drug identity. The Study PI and study physician(s) will make the decision to un-blind the identity of the study medication in the event that the study blind needs to be broken to make medical decisions regarding subject treatment.

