#### Medication accountability

The site principal investigator (PI) or designated study personnel will maintain a log of all study medication and record of dispensing of all medication to the subject. The site PI or his staff will count the tablets remaining at the end of the study and record the tablet count on the appropriate drug accountability form. Subject compliance with study medication will be assessed by comparing unused capsule count to dispensing logs and dosing records (number of tablets dispensed, number of tablets prescribed, versus the number returned). Subjects will also be asked to account for any missing tablets. If the bottles are not returned, the subject will be asked to report daily drug self-administration.

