### Medication Visit #2

After the 7-14 day washout period subjects will return to the lab to receive study medication prior to the alcohol challenge #2. Subjects will complete the same tests and interviews completed during the randomization visit (See appendix A for schedule of events). Based on the assessments at medication visit #2, subjects be discontinued for the following reasons: pregnancy, recreational drug use except for marijuana, evidence of non-compliance with study medication, suicidal thoughts or behavior, and use of a new medication that would make participation unsafe. Subjects will receive a 12-day supply of study medication and will be scheduled for the alcohol challenge #2. Subjects will be allowed to delay start of medication for up to 7 days after randomization in order to accommodate scheduling for the alcohol challenge trial.

Alcohol Challenge Trials 1 & 2: Subjects will return to the laboratory on day 12 of drug exposure for each medication trial to complete the alcohol challenge. For safety reasons, subjects will be asked to arrange transportation plans (no driving) prior each of the alcohol challenge trials. There will be a 7-14 day washout period between alcohol challenge Trial 1 and medication visit #2. The washout may extend to 14 days to accommodate the scheduling of the medication visit. Concomitant medications, urine drug screening, urine pregnancy testing, blood alcohol level will be assessed to determine eligibility to proceed with the challenge. Blood alcohol level must be 0.000 to continue with the study procedures. Urine collected for drug screening will be exposed to ultraviolet light as an objective test of medication compliance. If no fluorescence is observed in the urine sample the subject will be excluded from continuing with the challenge. Measures of drinking (TLFB) and cravings (OCDS, VAS and AUQ) will be collected to inform secondary outcomes. Subjects will be observed taking the morning dose of pitolisant (or placebo) on the day of the challenge (after compliance is confirmed via a urine screening). The peak plasma concentration of pitolisant should be reached approximately 60 minutes after administration. The alcohol self-administration session will begin no sooner than one hour after the administration of the observed 17.8 mg morning dose. The alcohol selfadministration will be conducted in the GCRU. The room will be a carpeted and furnished with

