Alcohol self administration Blocks 1 and 2. In each of the alcohol self-administration Blocks, subjects will be presented with four drinks, each mixed to raise their BAL 0.0125g/dl. They will be told that they can either consume the desired number of drinks over the following 60 minutes or they will receive the equivalent dollar amount of the cost of each drink (\$3.00) they did not consume before leaving the clinic. At the end of each 1 hour session the tray with the remaining drinks will be removed and the amount of alcohol remaining will be measured. Cravings will be assessed using the AUO and VAS and effect of pitolisant on stimulant effects of alcohol will be assessed using the BAES every 30 min during the self-administration blocks. Based on the rate of alcohol metabolism over the time of the trial, we anticipate that subjects who consumed every drink could reach a BAC of 0.09 to 0.13 g/dl depending upon differences in alcohol metobolism. Safety assessments will be completed (intoxication, sedation, adverse effects) prior to subjects leaving the laboratory. Subjects will be required to have a plan for transportation home that does not involve driving. Subjects will not be released until their blood alcohol level is  $\leq 0.04$  g/dl and they are not behaviorally impaired. After the second alcohol self-administration trial has been completed subjects will receive a copy of the NIAAA publication Rethinking Drinking and will be encouraged to review rethinking drinking materials online.

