### 12.2 Sample Size Determination

A group size of 28 completers was selected for use in this study based on an assumed effect size of 0.7 suggested by similar alcohol self-administration studies with amount consumed as the primary outcome. This effect size is in the range we found for the anticonvulsant zonisamide used in a similar alcohol self-administration study. The sample size for this study is based on an estimated reduction of 1.5 standard drinks with an estimated standard deviation (2.1) of the between Challenge Trial differences in alcohol self-administration, with an effect size of this magnitude (i.e. 0.7). This requires a sample size of 28 to allow for detection of a significant within-subject difference in alcohol consumption with an alpha value of 0.01 and power value of 0.81. Based on an estimated 15-20% rate of non-completion for randomized subjects, we anticipate randomizing 36 subjects to achieve a sample of 28 completers. Given our experience with recruiting AUD populations into clinical trials, we expect a screening exclusion rate of roughly 50%. Approximately 72 subjects will be consented and screened in clinic to yield a sample of 36 eligible subjects. Given that this a laboratory based experiment we do not plan to conduct any planned interim analyses in this study.

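### The labeling and blinding sections contradict each other on whether the bottle label names the treatment; the labeling rule, followed literally, would break the blind

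*Combined protocol and SAP*

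**What the plan says.** Section 5 declares the design: "This is a double-blind, randomized, placebo-controlled, crossover design trial". Section 8 then describes the bottle label twice.

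- **Medication Labeling:** "The label will include the drug name (e.g., 'Pitolisant 4.45 mg', 'Pitolisant 17.8 mg' or 'placebo". The same label carries a randomization number, a tablet count, storage conditions, the site's 24-hour telephone number, and spaces for the subject number and dispensing date.
- **Medication Blinding and Unblinding:** active and placebo capsules look identical, and "the bottle labels will not reveal the drug identity". The PI and study physicians decide when the blind is broken for medical reasons.

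The bottles reach the subject: "Medication will be dispensed to each subject in two bottles" (Study Medication). Site personnel keep the dispensing log, and under Medication accountability the PI or "staff will count the tablets remaining at the end of the study". On the challenge day, section 9 adds: "Subjects will be observed taking the morning dose of pitolisant (or placebo) on the day of the challenge".

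**The concern.** A bottle marked *placebo* discloses its contents, so the two rules cannot both be followed. If the pharmacy prints from the labeling section, the subject and any staff member who handles the bottle know the treatment for that period. Each subject receives both treatments, so they also know it for the other period.

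The outcomes make this serious. The primary outcomes in section 4.2.1 are the amount drunk and craving on the VAS and AUQ. The first is the subject's own choice between a drink and $3.00; the second is self-report. A subject who knows which period is active may drink less, or report less craving, because that is what is expected. That shift would coincide exactly with treatment. The section 12.1 model for consumption has terms for treatment, time block and trial order, and none of them can separate expectation from pharmacology.

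**Working it through.** **1. Do the two sections describe the same label?** Yes. The label in the labeling section has spaces for subject number and dispensing date and carries the site's emergency number. Those belong on a dispensed bottle, not on pharmacy stock. The blinding section also refers to the bottle labels.

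**2. Does other text reconcile them?** Section 2, section 5, the rest of section 8 and section 9 were read for this. None describes a tear-off, two-part, masked or pharmacy-only label. Matched capsules do not help if the bottle names what is inside.

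**3. How many labels?** Up to 36 randomized subjects (section 12.2) × 2 periods × 2 bottles per period = 144.

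**4. Who sees them, and when?** The subject keeps the bottles through each exposure period, and staff count what is left. The 17.8 mg bottle holds 5 pills for days 8 to 12, and the challenge is on day 12. With full adherence and no replacement supply, the observed dose before the drinking session is the last pill from that bottle. A missed dose would change this, and the contradiction does not depend on it.

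**5. What could expectancy do to the test?** The documents give no expectancy effect, so this step is an illustration. Inputs from section 12.2 are 28 completers, alpha 0.01, and an "estimated reduction of 1.5 standard drinks with an estimated standard deviation (2.1") for the between-trial differences. A paired t-test is used as a simple stand-in for the planned mixed model, and every completer is taken to be unblinded.

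- *The plan's figure.* 1.5 / 2.1 = 0.71, which the plan gives as 0.7. At effect size 0.7, a two-sided paired t-test with n = 28 and alpha 0.01 has power 0.815; the plan states 0.81. The plan does not say whether the test is one- or two-sided, but a one-sided test would give 0.883, so two-sided is assumed.
- *Smallest significant difference.* SE = 2.1 / √28 = 0.397. The critical value t(27, 0.995) is 2.771, and 2.771 × 0.397 = 1.10 standard drinks.
- *Rejection probability with no drug effect and an assumed shift b.* This is the noncentral t with 27 degrees of freedom and noncentrality b / 0.397:

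| Assumed shift b (standard drinks) | Noncentrality | Probability of a significant result |
|---|---|---|
| 0 | 0 | 1.0% |
| 0.25 | 0.63 | 2.4% |
| 0.5 | 1.26 | 8.2% |
| 0.75 | 1.89 | 21% |
| 1.0 | 2.52 | 42% |

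**6. Does the design bound the bias usefully?** No. In each block "subjects will be presented with four drinks, each mixed to raise their BAL 0.0125g/dl", so two blocks cap a session at 2 × 4 = 8 drinks and the difference at ±8. That is too wide to reassure, and those drinks are not the same unit as the standard drinks in section 12.2.

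**The case against.** The strongest reply is that the labeling sentence is loose shorthand for a combined label. It introduces the names as examples. Its placebo entry carries no strength, although placebo comes in two forms (25 mg and 50 mg riboflavin), so it reads more like a list of possible contents than a label scheme. Elsewhere, sections 8 and 9 describe each bottle as holding pitolisant of a given strength or placebo, which is the combined form. The section devoted to blinding states the masked outcome outright, and its unblinding provision presupposes that the bottle does not disclose the treatment. On this view the point is a drafting conflict whose intended answer is already known.

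Much of that is fair as evidence of intent, and it is why no claim is made that anyone was unblinded. It does not reconcile the text. The three examples are quoted separately, with the conjunction outside the quotation marks. The labeling section is also the operative instruction on label content, whereas the blinding section states only a result. If a combined label was meant, the sentence the pharmacy prints from should say so.

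It is also fair that the shifts in the table are assumed, that the documents give no basis for their range, and that any bias would raise the rejection rate. The figures show how sensitive the test is; they are not evidence that bias exists. The contradiction rests on none of them.

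**Conclusion.** The concern holds. The two sections give incompatible instructions for the dispensed bottle label, and no other text resolves them. This must be corrected, because masking is the main protection for outcomes the subject controls or reports.

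The consequence is conditional on the labeling sentence being followed as written. In that case up to 144 labels would name the treatment and both periods would be known. The size of the resulting bias cannot be estimated from the documents. Under the stated assumptions (two-sided paired t-test, all 28 completers unblinded, no drug effect), shifts of 0.25 to 1.0 standard drinks would raise the false-positive rate from 1% to between 2.4% and 42%.

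**What to change.** Replace the labeling sentence so that every bottle of a given strength carries the same text whichever treatment it holds, for example 'Pitolisant 4.45 mg or placebo' and 'Pitolisant 17.8 mg or placebo', together with the randomization number already planned for the label. State that the investigational pharmacy holds the treatment code and that it remains available for the emergency unblinding the protocol already provides for.

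The cost is one replaced sentence, a short statement on where the code is held, and a matching change to the pharmacy's label template. The pharmacy already packages the medication, so no subjects, visits or procedures are added.

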#### Medication Blinding and Unblinding

Study medication and placebo capsules will be identically matched in appearance and the bottle labels will not reveal the drug identity. The Study PI and study physician(s) will make the decision to un-blind the identity of the study medication in the event that the study blind needs to be broken to make medical decisions regarding subject treatment.

#### Medication accountability

The site principal investigator (PI) or designated study personnel will maintain a log of all study medication and record of dispensing of all medication to the subject. The site PI or his staff will count the tablets remaining at the end of the study and record the tablet count on the appropriate drug accountability form. Subject compliance with study medication will be assessed by comparing unused capsule count to dispensing logs and dosing records (number of tablets dispensed, number of tablets prescribed, versus the number returned). Subjects will also be asked to account for any missing tablets. If the bottles are not returned, the subject will be asked to report daily drug self-administration.

#### 9 Study Procedures

*Study Overview:* Each subject will complete 5 clinic visits over a period of up to 66 days of participation. Study participation is comprised of a baseline assessment, randomization visit, alcohol self administration Trial 1, an assessment visit to verify continued eligibility and dispense medication, and a second alcohol self-administration Trial (see figure 1 for an overview of study participation).

**Baseline assessment:** Consenting subjects will undergo a general medical screen, physical examination, and electrocardiogram. Drinking will be assessed using the TLFB, alcohol withdrawal using the Clinical Institute Withdrawal Assessment, and suicidality using the Columbia-Suicide Severity Rating Scale (C-SSRS). Exclusionary mental health conditions will be assessed using the MINI Neuropsychiatric Interview and SCISD-R Interview for DSM-5. Subjects will undergo laboratory testing that includes liver function and renal function, complete blood count, electrocardiogram recording, urine toxicology and a urine pregnancy test for women of child bearing potential.

Study randomization (medication visit #1): Qualified subjects will return to the lab within 14 days for randomization to a crossover sequence of drug exposure. Subjects will be assigned to one of 2 groups (n=18), with one group receiving pitolisant prior to the first alcohol challenge trial and the other receiving pitolisant prior to the second alcohol challenge trial. Randomization of subjects will be accomplished using a stratified randomization procedure that will allow for between-group balance for drinking status (heavy vs. very heavy). Heavy drinking is defined as  $\geq 21$ and < 35 standard drinks per week for men, and  $\geq 14$  and < 28standard drinks per week for women. Very heavy drinking is

Figure 1. Overview of Participation Baseline Consent and Screening 1-14 days Randomization Dispense Pitolisant/PLA 0-7 days Titration to target dose 2 X 4.45mg/day for 7 days 1 X 17.8mg for 5 days 0 days Trial 1 Alcohol Self Administration 7-14 day washout **Trial 2 dispense** Confirm eligibility Dispense pitolisant/PLA 0-7 days Titration to target dose 2 X 4.45mg/day for 7 days 1 X 17.8mg for 5 days 0 days Trial 2 Alcohol Self Administration

defined as  $\geq$  35 standard drinks per week for men, and  $\geq$  28 standard drinks per week for women. This stratified randomization will minimize the possibility that the order of study drug administration seems to influence outcomes when order effects are actually related to differences in severity of drinking between the two groups of subjects who are receiving the study medication in a different order. On the day of randomization, subjects will undergo an alcohol breath test, urine drug screening, urine pregnancy testing, assessment of concomitant medications, and the TLFB to ensure eligibility. Subjects who have purposefully abstained from drinking and achieved 14 days of abstinence prior to the challenge will be discontinued from participation for ethical reasons. Eligible subjects will be randomized and will receive a 12-day supply of over-encapsulated pitolisant or a matched placebo. Subjects will be scheduled for an alcohol challenge trial within 19 days of randomization. Subjects will be contacted to remind them to start taking study medication twelve days prior to the scheduled alcohol challenge trial. Subjects will be allowed to delay start of medication for up to 7 days after randomization in order to accommodate scheduling for the alcohol challenge trial.

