## 12.1 Study Hypotheses and Planned Analyses

HypothesisProposed Analyses1. Subjects will consume less alcohol during an alcohol self- administration trial when receiving pitolisant compared to when they are receiving placebo.The volume of alcohol consumed during alcohol challenge trials 1 and 2 will be used to test the effect of pitolisant on alcohol consumption. We will use a mixed models repeated measures approach to test for differences between alcohol consumed between the pitolisant and placebo self-administration trials45- 46. This data will be divided into first and second-hour blocks of self-administration. Within-subject factors for this analysis will include treatment and Time Block. Trial order will be used as covariate in these analyses to allow evaluation as to whether the order of treatments had a significant effect on the outcome. Appropriate covariance structures will be determined using

 
Subjects will consume less alcohol during an alcohol during an alcohol self-administration trial when receiving pitolisant compared to when they are receiving placebo.
 
The volume of alcohol consumed during alcohol challenge trials 1 and 2 will be used to test the effect of pitolisant on alcohol consumption. We will use a mixed models repeated measures approach to test for differences between alcohol consumed between the pitolisant and placebo self-administration trials45-46. This data will be divided into first and second-hour blocks of self-administration. Within-subject factors for this analysis will include treatment and Time Block. Trial order will be used as covariate in these analyses to allow evaluation as to whether the order of treatments had a significant effect on the outcome. Appropriate covariance structures will be determined using
 

 
less alcohol during an alcohol self-administration trial when receiving pitolisant compared to when they are receiving placebo.
 
1 and 2 will be used to test the effect of pitolisant on alcohol consumed between the pitolisant and placebo self-administration trials45-46. This data will be divided into first and second-hour blocks of self-administration. Within-subject factors for this analysis will include treatment and Time Block. Trial order will be used as covariate in these analyses to allow evaluation as to whether the order of treatments had a significant effect on the outcome. Appropriate covariance structures will be determined using
 

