include treatment and Time Block. Trial order will be used as covariate in these analyses to allow evaluation as to whether the order of treatments had a significant effect on the outcome. Appropriate covariance structures will be determined using
covariate in these analyses to allow evaluation as to whether the order of treatments had a significant effect on the outcome. Appropriate covariance structures will be determined using
order of treatments had a significant effect on the outcome. Appropriate covariance structures will be determined using
Appropriate covariance structures will be determined using
Akaikes information criteria to evaluate the best model fit.
Results analysis will be examined for both treatment effects and
the Treatment x Time Block interaction results.
2. Subjects will report Craving measures (AUQ and VAS) collected at 30-minute
lower levels of craving as intervals during the self-administration trials will be used to test
measured by the Visual the effect of pitolisant on alcohol craving. A mixed models
Analog Scale (VAS) and approach will be used to test for differences in craving between
the Alcohol Urge the pitolisant and placebo self-administration trials. Within-
questionnaire (AUQ) subject factors for this analysis will include Treatment and Time
during the pitolisant self- Block. Trial order will be used as covariate in these analyses to
administration trial allow evaluation as to whether the order of treatments has a
compared to the placebo significant effect on the outcome.
self-administration trial.
3. Subjects will BAES scores and BALs obtained during the 40-minute
experience no difference observation period and both of the 60-minute self-administration
in alcohol-induced blocks will be used to test the effect of pitolisant on the
stimulation, as measured stimulating effects of alcohol. A mixed model for repeated
on the BAES, after the measures approach will be used to test for differences between
consumption of the pitolisant and placebo on the stimulant BAES scores at each of
priming dose of alcohol the 10-minute observation intervals and 30-minute self-
when they are receiving administration intervals. This data will be analyzed with
pitolisant as compared to Treatment and Time used as within-subject factors.
when they are receiving
placebo.
5. Subjects will report The alcohol VAS, OCDS, and the TLFB measurements during
lower levels of alcohol the twelve-day period of drug exposure will be used to determine

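### The sequence randomization is stratified by drinking status to protect the order comparison, but the models that evaluate order omit the stratum; if order is coded as sequence, that check is needlessly conservative.

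*Combined protocol and SAP*

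**What the plan says.** Section 9 (study randomization) sets up a two-sequence crossover: "Subjects will be assigned to one of 2 groups (n=18"). Assignment uses a "stratified randomization procedure that will allow for between-group balance for drinking status (heavy vs. very heavy"), with sex-specific cut-offs in drinks per week. The reason follows in the same section: "This stratified randomization will minimize the possibility that the order of study drug administration seems to influence outcomes" when the real cause is "differences in severity of drinking between the two groups of subjects who are receiving the study medication in a different order".

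For alcohol volume (hypothesis 1), section 12.1 gives the model terms: "Within-subject factors for this analysis will include treatment and Time Block". It continues: "Trial order will be used as covariate in these analyses to allow evaluation as to whether the order of treatments had a significant effect". The craving model (hypothesis 2) has the same two within-subject factors and the same order covariate. No model in section 12.1 names drinking status, baseline drinking or the stratum. The models for hypotheses 3, 5 and 6 name neither order nor stratum.

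Section 12.2 plans 36 randomized subjects and 28 completers.

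**The concern.** The protocol treats drinking severity as able to imitate an order effect and balances it between the sequence groups for that reason. The models that evaluate order then leave it out.

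A comparison of two sequence groups is judged against variation between subjects. Balance removes the stratum's contribution from the estimated order difference, but the stratum's variance stays in the error term unless the model contains it. The reported standard error is then larger than the design warrants, and a real order effect is easier to miss.

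Trial order is the only order or carryover check named in section 12.1, in a two-period crossover with a washout of 7 to 14 days. With about 14 completers per sequence it has limited power to begin with.

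**Working it through.** **1. The plan's own figure.** Section 12.2 gives effect size 0.7, alpha 0.01, 28 completers and power 0.81. A two-sided paired t-test (noncentral t, 27 df) gives power 0.815, and 28 is the smallest number reaching 0.81. The figure reproduces. It rests on within-subject differences, so the stratum does not enter it.

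**2. Which test is affected.** One simulated data set was fitted with a mixed model (28 subjects, two strata of 14, assumed variances), with and without the stratum.

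| Term | SE without stratum | SE with stratum |
|---|---|---|
| Treatment (order as sequence) | 0.2847 | 0.2847 |
| Order coded as sequence | 0.6624 | 0.6462 |
| Order coded as period | 0.2021 | 0.2021 |

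Only the sequence-coded order term changes.

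**3. Size of the gain, first basis.** Let R2 be the share of the residual variance of subject means (averaged over both periods) that the stratum removes. This is an assumption, because the documents give no value. With the stratum balanced across sequences:

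SE ratio (with / without) = sqrt[(1 − R2) × (n − 2)/(n − 3)]

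| R2 | n = 36 (factor 34/33) | n = 28 (factor 26/25) |
|---|---|---|
| 0 | 1.015 | 1.020 |
| 0.10 | sqrt(0.927) = 0.963 | sqrt(0.936) = 0.967 |
| 0.20 | sqrt(0.824) = 0.908 | sqrt(0.832) = 0.912 |
| 0.30 | sqrt(0.721) = 0.849 | sqrt(0.728) = 0.853 |

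The standard error falls by about 3-4%, 9% or 15%. At R2 = 0 it rises by 1.5% (n = 36) or 2% (n = 28).

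**4. Size of the gain, second basis.** The shares may instead refer to true between-subject variance. They must then be scaled down, because a two-period mean also carries within-subject noise. With between-trial correlation rho, true between-subject variance is 2·rho/(1 + rho) of the variance of a two-period mean. At rho = 0.5 (assumed) this is 1/1.5 = 0.667.

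The plan's SD of differences, 2.1, gives the same share. Total variance is 2.1²/(2 × 0.5) = 4.41. The variance of a two-period mean is 4.41 × 0.75 = 3.31, and the between-subject part is 4.41 × 0.5 = 2.21.

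Shares of 10%, 20% and 30% become effective R2 of 0.067, 0.133 and 0.20. With n = 36 the ratios are:
- sqrt(0.933 × 34/33) = 0.981
- sqrt(0.867 × 34/33) = 0.945
- sqrt(0.80 × 34/33) = 0.908

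The falls are about 2%, 6% and 9%. They are about 1%, 3% and 6% at rho = 0.3, and about 3%, 7% and 12% at rho = 0.7.

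**5. Effect on the order test.** Simulation used 28 completers, a stratum balanced between sequences and split equally, a two-sided 0.05 test, and 40,000 runs per setting. R2 is the true share of the variance of subject means. Power is for an order effect of 1 SD of subject means.

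| R2 | Type I error without / with | Power without / with |
|---|---|---|
| 0.10 | 0.041 / 0.052 | 0.73 / 0.76 |
| 0.20 | 0.028 / 0.050 | 0.74 / 0.81 |
| 0.30 | 0.019 / 0.049 | 0.74 / 0.86 |

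Without the stratum the test is conservative. With it, the type I error is close to nominal.

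**The case against.** **The coding is not settled.** The protocol calls the two challenge sessions Trial 1 and Trial 2, so trial order could mean period. The test would then be within-subject and the stratum irrelevant to it. Section 12.1 speaks of the order of treatments, and section 9 describes two groups receiving medication in different orders. Both favour sequence, but the coding is never stated. This stands, so the point is conditional on it.

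**Stratification already does its stated job.** Its purpose is to prevent a false order effect. Balance achieves that, and the unadjusted test errs on the safe side. With exact balance the order estimate is the same either way. This stands too. What is lost is power to see a real order effect, which is not the protocol's stated reason for stratifying.

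**A large R2 is doubtful.** All subjects are heavy drinkers by entry criteria, the stratum is a two-level cut, and intake is capped at eight drinks, each mixed to a fixed blood-alcohol increment. Section 9 shows that severity was thought worth balancing, not how much variation it explains. The upper end of the range is therefore an assumption only.

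**Little depends on the result.** The plan attaches no decision rule to the order evaluation.

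A reader might also infer that the primary treatment comparison is biased or underpowered because the stratum is missing. The documents do not support that. In complete pairs each subject is their own control, the stratum cancels, and the calculation behind 28 completers is unchanged.

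**Conclusion.** The omission is real and minor. It concerns the order check in the consumption and craving models, and only if trial order is entered as sequence. In that case the standard error for order is wider than necessary and the test is conservative.

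The gain from adding the stratum is about 3-4%, 9% or 15% of that standard error if the stratum explains 10%, 20% or 30% of the variance of subject means. It is about 2%, 6% or 9% if those shares refer to true between-subject variance and the between-trial correlation is 0.5. All shares and correlations are assumptions, and with no prognostic value there is a small loss. Subjects who complete only one period contribute between-subject information to the mixed model, so the treatment estimate may gain slightly through them.

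It would be too strong to say that the order test is certainly between-subject, or that the stratification fails in its purpose. The text leaves the coding open, and balance by design meets the stated aim.

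**What to change.** Before unblinding, make two changes to the models for hypotheses 1 and 2 in section 12.1:

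1. Add the randomization stratum (heavy, very heavy) as a fixed effect.
2. State that trial order is entered as treatment sequence, and enter period (first or second challenge) as a separate term.

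The stratum is already recorded at randomization, so no new data are needed. It costs one between-subject degree of freedom, which is the 1.5-2% widening above if drinking status proves uninformative. The period term takes one within-subject degree of freedom. For the planned 28 completers this moves the power of the paired comparison from 0.815 (27 df) to 0.813 (26 df). The sample size stays as it is.
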